9.3 Variables

The sections below describe the theoretical aspects of relevant variables. Data sources and operational definitions are discussed in [Section 9.4](#).

9.3.1 Exposure of Interest

This pregnancy registry is strictly observational, and prior Menveo vaccination is a condition of enrollment. Menveo vaccination is not indicated in pregnancy. Therefore, Menveo vaccination exposure in pregnancy is expected to be inadvertent and to occur within 28 days of conception or in early pregnancy. Data to be collected include the date of vaccination, facility (e.g., HCP office, clinic, or commercial facility such as a pharmacy or other retail outlet), dose, and lot number if available.

9.3.2 Outcome(s) of Interest

MCM: The registry defines and codes MCMs with criteria specified by CDC MACDP ([CDC, 2007](#)). The registry defines an MCM as any major structural or chromosomal defect or combination of 2 or more conditional defects in live-born infants, stillbirths, or fetal losses of any gestational age (including outcomes prior to 20 weeks' gestation or birth weight <500 g). This definition is consistent with, but not restricted to, the CDC MACDP definition. Clusters of conditional abnormalities (as defined by CDC MACDP) and data from aborted fetuses of less than 20 weeks' gestation, when available, will be included to increase sensitivity of monitoring. The MACDP includes conditional defects only if in the presence of a major defect. This registry will consider reports of 2 or more conditional defects as a defect case, to increase signal sensitivity and to capture instances where a combination of conditional events might constitute a major defect or syndrome.

The registry conforms to the CDC MACDP guidelines in disqualifying as defects those findings that are present in infants born at less than 36 weeks of gestation and are attributable to prematurity itself, such as patent ductus arteriosus, patent foramen ovale, or inguinal hernias. The CDC MACDP classification does include chromosomal defects. Though these defects are not likely to contribute to a risk for a vaccine exposure, the registry includes these defects to maintain this consistency with the CDC MACDP.

Live-born infants with only transient or infectious conditions or with biochemical abnormalities will be classified as being without reported MCMs unless there is a possibility that the condition reflects an unrecognized MCM. Detected and reported transient or infectious conditions or biochemical abnormalities in infants without reported MCMs and defects that are excluded by the CDC guidelines will be noted in an appendix in the registry reports.

Preterm birth: An infant born at gestational age <37 weeks

LBW: An infant whose birth weight is <2500 g

9.3.3 Other Variables

Maternal characteristics: Age, ethnicity, race

Prenatal data: Last menstrual period (LMP), estimated date of delivery (EDD), corrected estimated date of delivery (CEDD)

Prenatal tests: Name of test, date of test, result

Obstetrical history: Previous pregnancies, live births, stillbirths, SABs, induced abortions (IABs), births with congenital malformations, family history of congenital malformations

Concomitant medical conditions

Concomitant medications and vaccines

Alcohol, tobacco, and illicit drug use

Pregnancy outcomes

Each pregnancy outcome will be classified in 1 of the following mutually exclusive categories:

- Live birth: an infant born alive
- Stillbirth: a fetal death occurring at 20 weeks' gestation or greater, or if gestational age is unknown, a fetus weighing 500 g or more
- SAB: fetal death or expulsion of products of conception prior to 20 weeks' gestation. Terminology may include missed abortion, incomplete abortion, and inevitable abortion.
- IAB: voluntary interruption of pregnancy, including pregnancy termination that occurs electively, to preserve maternal health, or due to fetal abnormalities

- Ectopic pregnancy: implantation of a conception outside of the uterus
- Molar pregnancy: a conception that results in a gestational trophoblastic tumor

Infant Outcomes: Gestational age, birth weight, sex

Maternal Information

- Maternal demographics (age, ethnicity, race)
- LMP
- EDD determined from LMP
- CEDD (e.g., by ultrasound), if available
- Prenatal tests (diagnostic or screening) performed, date of test, and findings including the identification of congenital anomalies

Maternal Obstetrical History

- Number of previous pregnancies
- Outcome of previous pregnancies: live births, stillbirths, SABs, IABs, ectopic pregnancies, molar pregnancies
- History of offspring with congenital anomalies
- Maternal and paternal history of congenital anomalies

Maternal Menveo Exposure (may be provided initially by the pregnant woman at registry enrollment and confirmed by the vaccinating HCP)

- Menveo administration, including dose, timing, and lot number

Other Conditions and Exposures

- Concurrent maternal conditions
- Concomitant medications taken during pregnancy
- Tobacco, alcohol, and illicit drug use during pregnancy

Pregnancy Follow-up

Around the end of the second trimester and in the month of the EDD, the ***Interim Pregnancy Follow-up Form*** and ***Pregnancy Outcome Form*** (respectively) will be requested from the obstetric HCP.

Information Collected at Interim Pregnancy Follow-up and Pregnancy Outcome

Follow-up at End of Second Trimester

Pregnancy Status

- Updates to EDD (ie, CEDD)
- Subsequent prenatal tests (diagnostic or screening) performed and findings including the identification of congenital anomalies
- Pregnancy complications (preterm labor, eclampsia, placental abruption)
- Details of pregnancy outcome if pregnancy is not ongoing as described below

Other Exposures

- Concomitant medications
- Tobacco, alcohol, and illicit drug use during pregnancy

Additional Information Collected at Pregnancy Outcome

Fetal Outcome

- Pregnancy outcome (live birth, stillbirth, SAB, IAB, ectopic pregnancy, molar pregnancy)
- Date of outcome of pregnancy
- Gestational age at outcome
- Fetal/infant characteristics: sex, birth weight
 - MCM(s) and assessment of potential contributing factors
 - For a fetal loss (SAB, stillbirth), factors that may have had an impact on the fetal loss and attribution

Targeted Follow-up Process

If there is an MCM or other event of interest noted, in order to properly characterize the event, additional information may be requested from the reporting HCP on the ***Targeted Follow-up Form***:

- Details of the MCM/condition
- Etiology
- Outcome attribution
- Specific questions requested by NVD and/or the MCM evaluator

Attempts to Obtain the Follow-Up Information

In the month that the follow-up is due, the HCP will be contacted and asked to provide follow-up information. Three subsequent attempts, as necessary, will be made every 2 weeks via various modes of communication. If there is still no response from the provider, a final communication will be sent indicating the case is lost to follow-up. If this communication prompts a response from the HCP or the requested data is later received, the case will be re-opened and assessed for evaluability. If, at any point in the follow-up process, the reporter indicates that the patient is lost to follow-up, no further attempts will be made.

Follow-Up Process for Clarification of Information

For critical data points, if there are outstanding questions, discrepancies between forms, or missing data, the appropriate reporter will be contacted for clarification. Three subsequent attempts, as necessary, will be made every 2 weeks. If no further information is obtained on an otherwise evaluable case, the discrepant information in the data fields may be left blank, identified as “unspecified.” On a case-by-case basis, qualified registry staff or the principal investigator may make a determination on discrepant information (e.g., determination of partially illegible word or illogical year).

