9.2 Setting

9.2.1 Study Period

The pregnancy registry will be implemented after approval by applicable regulatory authority and central institutional review board (IRB). The target enrollment goal of the registry is 100 prospectively enrolled pregnant women. The data collection process for each participant will begin at enrollment (during pregnancy), and follow-up will occur at the end of the second trimester (approximately 24 weeks' gestation) and at pregnancy outcome (delivery or early termination).

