9.7 Data Analysis

Registry Case Management and Disposition

Prospective Registry Reports

The registry will encourage prospective registration, which is defined as registration of a pregnancy exposure prior to knowledge or perceived knowledge of the pregnancy outcome (e.g., structural defect or genetic abnormality noted on a prenatal test). Those with no abnormalities identified on a prenatal test prior to enrollment will be considered prospective and included in the analysis. The rationale, potential bias, and analytic techniques to address any bias that may be introduced by this practice are addressed in [Section 9.7.4](#).

Data from HCP provider networks and HMOs that provide de-identified data on all exposed pregnancies in their network will fall into the category of prospective registry reports, as these networks/HMOs provide objective data on every pregnancy exposure in the network/HMO, both positive and negative outcomes. Thus, they avoid the reporting bias inherent in retrospective reporting only after a negative outcome has been noted.

Retrospective Registry Reports

Retrospective reports will also include subjects for whom the pregnancy outcome has already occurred or an abnormality has been identified on a diagnostic or screening prenatal test prior to enrollment. Retrospective reports can be biased toward the reporting of more unusual and severe cases and are less likely to be representative of the general population experience than reports reported prior to knowledge of outcome. Therefore, retrospective reports will not be included in the primary analysis and statistical calculation of risk. Retrospective reports with reported MCMs and/or spontaneous fetal losses will be reviewed to aid in detection of early signals and listed in registry reports. Retrospective reports will not be actively solicited by the registry and will not be captured in the registry database unless a congenital anomaly is reported.

Loss to Follow-Up

For a prospective report or pregnancy where follow-up information on the pregnancy outcome (live birth, fetal loss, etc.) is never obtained or is unavailable, the pregnancy will be considered lost to follow-up. Subjects lost prior to pregnancy outcome will be tallied in the registry reports but not included in the statistical analyses.

Duplicate Registry Reports

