9.7.4 Statistical Considerations

Because early prenatal testing is so prevalent, it may be difficult to achieve adequate numbers of prospectively identified pregnant women if all pregnancies with prior prenatal

testing are excluded from the analysis. Therefore, the primary analysis will include pregnancies enrolled prior to outcome but after prenatal test as long as the test does not indicate an abnormality. However, this practice could potentially bias the results by lowering the overall risk of MCMs (Honein, 1999). The analysis will attempt to address bias introduced by this practice.

While the registry analysis will be limited primarily to prospective reports, some pregnancy exposures will be reported only following pregnancy outcome (retrospective cases). Each retrospective report will be carefully reviewed. In general, retrospective reports of exposures to vaccines or medication following notification of outcome are biased toward reporting of the severe and unusual cases and are not reflective of the general experience with the vaccine or medication. Moreover, information about the total number of exposed persons is not known. Therefore, rates of outcomes cannot be calculated from these data. However, a series of reported MCMs can be analyzed to detect patterns of specific MCMs and can identify early signals of vaccine or medication risks.

Those pregnancies that have reached EDD, but for which outcome information was unobtainable after 4 attempts, will be considered lost to follow-up. It is possible that outcomes among pregnancies lost to follow-up could differ from those with documented outcomes. Because of differences in individual reporting patterns, it is currently not possible to assess with any certainty what impact the potential biases the losses to follow-up may have on the analysis. However, efforts at comparing some of the characteristics of each group may be conducted in an attempt to address this potential source of bias.

Following the MACDP convention, calculation of MCM risk will exclude fetal losses (SABs, IABs, stillbirths, etc.) for which no MCMs have been detected as they may introduce a classification bias. The percentage of these pregnancies consisting of potentially normal outcomes or MCMs is unknown. The data collection form attempts to obtain information on MCMs detected at the time of the outcome. However, the reporting physician may not know the condition of the aborted fetus.

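### Outcome requests start in the month of the EDD and can precede delivery, so term births get fewer post-delivery attempts than preterm births and the observed preterm rate can be biased upward

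*Protocol*

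**What the plan says.** Section 9.2.1 places the last follow-up at the end of pregnancy: "and at pregnancy outcome (delivery or early termination". Section 9.4 (Pregnancy Follow-up) sets when the two follow-up forms are requested: "Around the end of the second trimester and in the month of the EDD". No day within the month is fixed.

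Section 9.4 (Attempts to Obtain the Follow-Up Information) gives the chasing rule: "In the month that the follow-up is due, the HCP will be contacted and asked to provide follow-up information". Then: "Three subsequent attempts, as necessary, will be made every 2 weeks via various modes of communication". If the provider still does not respond, "a final communication will be sent indicating the case is lost to follow-up". There is a safeguard for late data: if "the requested data is later received, the case will be re-opened and assessed for evaluability".

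Section 9.7.4 defines loss: "Those pregnancies that have reached EDD, but for which outcome information was unobtainable after 4 attempts, will be considered lost to follow-up". Section 9.7 (Loss to Follow-Up) states the consequence: "Subjects lost prior to pregnancy outcome will be tallied in the registry reports but not included in the statistical analyses".

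Neither section requires an attempt to follow delivery, and neither says how a reply that the woman is still pregnant counts.

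**The concern.** The trigger is the due date, but the information sought exists only after birth. By definition a preterm infant is born more than three weeks before the EDD, so nearly all requests reach an office that already knows the outcome. For a term birth, especially with an EDD late in the month or a delivery after the EDD, some requests come too early to be answered. The number of useful attempts therefore varies with gestational age at birth, which is what the preterm endpoint measures.

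Lost pregnancies are removed from numerator and denominator, and section 9.5 expects follow-up completion in pregnant adolescents to be very low. The analysed set could then be enriched for preterm infants, and the comparison with the national rate could lean towards a signal with no vaccine effect. The comparison of lost and evaluable women in section 9.7.2 covers demographic and baseline characteristics. It cannot reveal this, because gestational age at birth is not a baseline characteristic and is unknown for lost cases.

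**Working it through.** **Inputs from the protocol.** First contact in the EDD month, then +14, +28 and +42 days (9.4). Conception = EDD minus 38 weeks, so the EDD is 40 gestational weeks (9.4.1). Preterm is under 37 weeks (9.3.2), so the latest preterm birth is 36w6d, or EDD - 22 days. Reference rate 12.37%, n = 58, detectable ratio 1.99 (9.5). One-sample binomial, one-sided 5% (9.6.2).

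**Assumptions (the protocol gives no figures).** Response q per contact after delivery; a contact before delivery yields nothing; contacts are independent; EDD day uniform over the month; 12.37% preterm, with term births spread over 37-41 weeks.

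**Step 1: the plan's own figure.** With n = 58 and p = 0.1237, P(X >= 11) = 0.097 and P(X >= 12) = 0.0494, so the cut-off is 12. At 1.99 x 0.1237 = 0.246, P(X >= 12) = 0.799. The stated 80% power reproduces.

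**Step 2: dates.** For a first contact on day 1 of a 31-day month (the earliest possible), the attempts in days from the EDD are:

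| EDD falls on | Attempts |
|---|---|
| day 1 | 0, +14, +28, +42 |
| day 15 | -14, 0, +14, +28 |
| day 31 | -30, -16, -2, +12 |

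In the last row a birth on the EDD has one attempt after it. A preterm birth (EDD - 22 or earlier) can miss only the attempt at -30. The fourth attempt is never before EDD + 12 days (41w5d). In the model 0.04% of term births follow all four attempts with a day-1 start, and none with a mid-month or EDD-day start.

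**Step 3: effect on retention.** With k attempts after birth, P(outcome obtained) = 1 - (1 - q)^k. In the last row with q = 0.3, a birth on the EDD has k = 1 and retention 0.30. A birth at EDD - 25 has k = 3 and retention 1 - 0.7^3 = 0.657.

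**Step 4: averaged over EDD days and birth weeks.** With R_P and R_T the retention of preterm and term births:

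observed rate = 0.1237 R_P / (0.1237 R_P + 0.8763 R_T)

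Example, first contact on day 15, q = 0.2: R_P = 0.5904, R_T = 0.5418. This gives 0.0730 / (0.0730 + 0.4748) = 13.3%.

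| First contact | Mean attempts after birth, preterm / term | Observed, q = 0.5 | Observed, q = 0.2 |
|---|---|---|---|
| day 1 of month | 3.95 / 2.76 | 13.8% | 15.5% |
| day 15 | 4.00 / 3.54 | 12.8% | 13.3% |
| on the EDD | 4.00 / 3.71 | 12.6% | 12.9% |
| EDD + 28 days | 4.00 / 4.00 | 12.37% | 12.37% |

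Over q = 0.15 to 0.50, the day-1 start gives 13.8-15.8%. Mid-month, evenly spread and EDD-day starts together give about 12.6-13.6%.

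**Step 5: chance of 12 or more preterm among 58.** It is 4.9% at 12.37%, 5.5% at 12.6%, 8.8% at 13.6%, 9.6% at 13.8% and 19.7% at 15.8%.

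**Step 6: sensitivity (q from 0.7 down to 0.2, except the last item).**
- Counting the final communication as a fifth contact lowers the day-1 range from 13.0-15.5% to 12.6-14.4%.
- If offices can report only 14 days after birth and the final communication is ignored, the ranges rise to 12.8-15.2% (EDD-day start), 13.0-15.5% (day 15) and 14.9-20.0% (day 1).
- Section 9.5 expects about 15 women a year through the registry and about 60 from external sources. Read as 3 x 15 + 60 = 105, this is close to the target of 100. If those 60 are not chased in this way, the day-1 range for q = 0.15 to 0.50 falls to about 12.6-13.2%.

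**The case against.** The strongest reply is that the rule is less rigid than the model. Reminders are sent only as needed, and a case closes for lack of a response. An office that answers that the woman has not delivered has responded, and Table 9.4-1 lets pregnancy status be updated at the outcome contact. The form stays with the office, a final message follows, and late data re-open the case. External network and health-plan data are described as covering every exposed pregnancy, with no EDD-month chasing. The larger figures need every first contact on day 1, which the protocol does not say. Habitual non-responders would also weaken the link between number of attempts and retention. Finally, the registry calls itself descriptive, and the cut-off of 12 comes from the power calculation, not from a stated decision rule.

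Most of this stands as a limit on size. It does not remove the mechanism: section 9.7.4 counts failed attempts without asking whether an outcome existed to report, and re-opening helps only if someone later sends data. Section 9.7.4 concedes that losses may differ in outcome and that the effect cannot be assessed with certainty, which favours removing an avoidable cause.

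A reader might infer that attempts run out before many term births. The dates rule that out, since the fourth attempt is at least 12 days after the EDD. A reader might also see a contradiction with section 9.2.1. There is none: that section names the data point, while 9.4 says when the form is requested.

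**Conclusion.** The point holds in a limited form. The calendar trigger and the loss rule give term births fewer post-delivery attempts than preterm births, and excluding lost cases can then push the observed preterm rate upward. The likely size is small: about 0.2 to 1.2 percentage points above 12.37% for mid-month, evenly spread or EDD-day first contacts, and about 1.4 to 3.4 points only if every first contact is on day 1. Both ranges rest on assumed response rates of 15-50% per contact, an assumed birth-week distribution, and pre-delivery contacts being wasted. The bias shrinks if the final communication counts, if replies of not yet delivered keep the case open, or if external reports are not chased. It grows if offices report with a delay.

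It would be tempting to state the same bias for low birth weight. That was not modelled. The direction is probably the same, but weaker, because some low-birth-weight infants are born at term. The change is worth making because it is cheap and the planned baseline comparison cannot detect the problem.

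**What to change.** In section 9.4, send the first Pregnancy Outcome Form request at a fixed interval after the EDD, or the corrected EDD where available (for example 4 weeks), or earlier once the registry learns that the pregnancy has ended. In sections 9.4 and 9.7.4, count the four attempts towards loss to follow-up only from that date, so that a contact made before delivery is never a failed attempt. In the model, a start at EDD + 28 days gives four useful attempts to both groups and returns 12.37% at every response rate tried.

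The cost is a wording change in two sections and a new reminder date. Outcome data and close-out come about one month later, so the roughly 10 months allowed in section 6.0 for follow-up and cleaning would lengthen by the same amount.

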9.4.1 Operational Exposure Definition

Menveo administered 28 days prior to conception or at any time during pregnancy (from conception until pregnancy outcome) will constitute exposure. The 28-day window prior to conception corresponds with the time to immunologic response as indicated in the Menveo product label (Menveo package insert, 2012). Menveo exposure will be further categorized by earliest trimester of exposure. Menveo is not indicated in pregnancy and is typically given to adolescents and young adults. Thus, the vast majority of pregnancy exposures will be inadvertent first trimester exposures, most likely prior to recognition of the pregnancy. For this registry, gestational weeks will be estimated from the most

reliable EDD as reported by the HCP. If a CEDD is provided by the HCP, it will be used instead. The date of conception will be calculated as the most reliable EDD minus 38 weeks. If the EDD is not available or never estimated, the first day of the LMP may be used to estimate gestational age. The second trimester will be considered to begin at week 14 after the date of conception or LMP, and the third trimester, at week 28. If there is a discrepancy between gestational age calculated from LMP and reported gestational age, the HCP will be asked to verify the data.

When a pregnant woman enrolls in the registry, she will be asked when and where she was immunized with the Menveo vaccine. She will then be asked to provide a medical release that allows the registry to confirm Menveo vaccination with the appropriate source. The registry will contact the Menveo vaccination provider to confirm the vaccination date, brand, and lot number. If HCPs provide de-identified data to the registry, they must be able to verify the Menveo vaccination and date of vaccination.

